ⁱ The investigator must record all dates of leuprolide acetate administration in the electronic data capture (EDC) system. For the relugolix group, patients will self-administer relugolix at home. The investigator must call the patient to confirm the date that the patient first started taking relugolix and record this date in EDC.

^j Can be either in office or by telehealth, performed as needed per investigator discretion.

Protocol Amendment 2

- ^k Data collected during the discontinuation phase of the study will focus on the clinical status of the prostate cancer and therapy, concomitant medications, hospitalizations for any reason, emergency room visits, adverse events (serious adverse events or adverse events resulting in discontinuation of study drug) and change in cardiovascular risk factors. If the patient does not react to the e-mail-based follow-up questionnaire alerts, phone contacts with the study patients can be established as a reminder.
- ^l Selective safety data collected in this study will include serious adverse events and nonserious adverse events that lead to the discontinuation of relugolix or leuprolide acetate.
- ^m All concomitant medications currently being taken or were used by the patient within 30 days prior to signing the ICF will be recorded at baseline by the recruiting physician and reviewed by the study medical monitor and CRO. During the discontinuation phase of the study, new concomitant medications will be reported by patients via the email-based follow-up questionnaire.

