9.2. Analysis Populations

Safety population is defined as all randomized patients who are treated with at least one dose of relugolix or one injection of leuprolide acetate after the date of randomization to the study.

Safety population will be used to analyze other safety data including treatment-emergent adverse events and clinical laboratory tests as obtained per standard of care.

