1.1. Study Objectives and Endpoints

The study objectives are summarized in [Table 1](#).

Table 1: Study Objectives and Endpoints

Objectives	Endpoint
Objective	

To describe the safety of relugolix in the study population	
The safety of relugolix will continue to be assessed in the study population. 
Adverse events (AEs) as characterized by type, frequency, severity, seriousness, and relationship to study drugs

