4.2.1. Safety Population

Safety population is defined as all randomized patients who are treated with at least one dose of relugolix or one injection of leuprolide after the date of randomization to the study. Safety population will be used to analyze other safety data including treatment-emergent serious adverse events and clinical laboratory tests as obtained per standard of care.

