6.1. Adverse Events and Serious Adverse Events

Per protocol, serious adverse events will be reported by the patient (or, when appropriate, by a caregiver, surrogate, or the patient's legally authorized representative) using questionnaires submitted electronically. Serious adverse events will also be reported by the investigators electronically through the electronic data capture.

The severity of all treatment-emergent adverse events will be evaluated by the investigator based on the National Cancer Institute's Common Terminology Criteria for Adverse Events (NCI CTCAE v5.0) and will be coded to preferred term and system organ class using the Medical Dictionary for Regulatory Activities 25.1 or higher.

Treatment-emergent serious adverse event is defined as any serious adverse event that occur after administration of the first dose of study drug and prior to the end of the study.

Serious adverse event summaries will be based on treatment-emergent adverse events, unless otherwise specified. Listing for all serious adverse events will be provided.

Tabular summaries with the number and percentage of patients with the following adverse events (but not limited to) will be provided:

- Overview of adverse events
- All adverse events
 - By system organ class and preferred term
 - By decreasing frequency of preferred term
 - By decreasing frequency of preferred term and relatedness to study drug

- All serious adverse events
 - By system organ class and preferred term
 - By decreasing frequency of preferred term
- Serious adverse events leading to study drug withdrawn
 - By system organ class and preferred term
 - By decreasing frequency of preferred term
- Serious adverse events in fatal outcome
 - By system organ class and preferred term
 - By decreasing frequency of preferred term

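### SAP 6.1 names a withdrawal table, an AE listing and a treatment-emergent definition for serious events only, so the nonserious discontinuation events that the protocol collects go unidentified

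*SAP*

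**What the plan says.** **Collection.** Footnote l of the Schedule of Activities (protocol 1.3) defines the selective safety data as "serious adverse events and nonserious adverse events that lead to the discontinuation of relugolix or leuprolide acetate". Protocol 8.2 and the AE definitions in Appendix 2 give the same scope. Under 8.3.1.1, investigators enter nonserious discontinuation events in electronic data capture within 8 calendar days of site awareness. Appendix 2 has the CRO record both categories in the eCRF.

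**Analysis.** Protocol 9.3 leaves the detail of the AE analysis to the SAP. SAP 1.1 states the endpoint broadly: "Adverse events (AEs) as characterized by type, frequency, severity, seriousness, and relationship to study drugs". SAP 6.1 introduces its tables with "Tabular summaries with the number and percentage of patients with the following adverse events (but not limited to) will be provided". The list contains an overview, tables of all AEs (by class and term, by frequency, and by relatedness), tables of all serious AEs, fatal serious AEs, and one withdrawal item, "Serious adverse events leading to study drug withdrawn". The listing commitment is "Listing for all serious adverse events will be provided". The treatment-emergent definition begins "Treatment-emergent serious adverse event is defined as any serious adverse event that occur after administration of the first dose of study drug".

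**Populations.** Protocol 9.2 applies the safety population to other safety data, "including treatment-emergent adverse events and clinical laboratory tests as obtained per standard of care". The matching sentence in SAP 4.2.1 reads "including treatment-emergent serious adverse events and clinical laboratory tests as obtained per standard of care".

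**The concern.** Describing safety is now the study's only objective (protocol 3, SAP 1.1). With AE collection restricted to two categories, the nonserious category exists for one reason: to record why patients stopped drug without a serious event. A withdrawal table filtered to serious events omits that category, and the SAP nowhere names it.

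Two things are at stake. First, the study report could describe AE-related discontinuation by class and term without the nonserious causes. Second, tables titled as covering all AEs could be taken for overall AE incidence, when by design they hold serious events plus the nonserious events that stopped treatment.

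**Working it through.** The plan gives no figure on this point, and the legacy sample-size figures in SAP 2.2 do not bear on it. The check sets the collection rules beside the SAP 6.1 outputs.

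| Event category | In selective safety data? | Named withdrawal table | Promised listing | Treatment-emergent definition | All-AE tables |
|---|---|---|---|---|---|
| Serious, led to stopping | Yes | Yes | Yes | Yes | Yes |
| Serious, did not lead to stopping | Yes | Not applicable | Yes | Yes | Yes |
| Nonserious, led to stopping | Yes | **No** | **No** | **No** | Yes, not identified as a cause of stopping |
| Nonserious, did not lead to stopping | No | Not applicable | No | No | Absent, and the title does not say so |

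**Step 1: what the withdrawal table omits.** Let S be the number of patients with a serious AE that led to stopping. Let N be the number whose only AEs leading to stopping were nonserious.

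- Patients with any AE leading to stopping = S + N.
- Patients in the named table = S.
- Share not shown = N / (S + N).

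The documents give neither S nor N. If N = 0 the share is 0. If S = 0 and N > 0 the share is 100%. No narrower range can be derived. What can be said is that, under selective collection, every collected nonserious AE led to discontinuation, so the serious-only filter removes that whole category from the table.

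**Step 2: what the all-AE tables contain.** Under footnote l and the eCRF rule in Appendix 2, they contain serious AEs plus nonserious AEs leading to discontinuation. The fourth row of the table above is outside them by design. The documents do not say how many events that row would hold.

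**Step 3: the one sentence that reads wider.** Protocol 8.3.1 says that all AEs reported in the follow-up questionnaires are collected from consent to the final visit. Footnote k of the Schedule of Activities describes the questionnaires' AE content as serious events or events resulting in discontinuation. Protocol 8.3 has the CRO check the questionnaires for selective data, and Appendix 2 has it record those two categories. The narrower reading has more support, but the sentence has not been reconciled with the other passages.

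**Step 4: what a table of these events needs.** For nonserious events the SAP gives no treatment-emergent window. Relatedness may also have gaps. For events not submitted by the investigator, the causality section of Appendix 2 obliges the CRO to assess each serious event and states no such duty for nonserious ones. The recording section of the same appendix says more generally that reports are assessed for causality, so coverage of questionnaire-reported nonserious events needs confirming before the relatedness table is programmed.

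**The case against.** The table list is explicitly open-ended, so the sponsor may add a table. SAP 4.4 says reasons for stopping treatment will be summarized, so AE may appear there as a reason. The nonserious discontinuation events are not lost, since they fall within the all-AE tables. The withdrawal table is also correctly titled for what it contains. The study was stopped, the objective is descriptive, and the protocol states its selective collection openly. The difference between SAP 4.2.1 and protocol 9.2 is small: both sentences give examples, and SAP 6 covers adverse events as well as serious ones.

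Most of this stands as a limit on the size of the problem. It does not remove it. Permission to add a table does not prespecify one. SAP 4.4 leaves its categories to be defined and promises no class, term, severity or relatedness detail. It also uses the ITT population, although SAP 4.2 says only the safety population will be analyzed. The all-AE tables do not label an event as a cause of stopping, so a reader would have to infer it from the collection rule.

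**Conclusion.** The point holds as a missing table, listing, definition and label. The plan collects nonserious discontinuation events and then names no output that presents them as such. The share of AE-related discontinuations absent from the withdrawal table is unknown (0 to 100%). The conclusion rests on reading collection as selective, which protocol 1.3, 8.2 and Appendix 2 support. It should be corrected because safety description is all that remains of the study, but no hypothesis test or error rate is affected.

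A reader might infer more, and the documents do not support it:

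- **That the reported AE discontinuation rate is too low.** The SAP presents the table as serious events only and nowhere calls it the overall rate.
- **That most AEs are excluded, or that the all-AE percentage falls far below true incidence.** No figure supports either. Only the exclusion by design of nonserious events without discontinuation is established.
- **That the content of the all-AE tables depends on whether the patient or the investigator reported the event.** On footnote k and the eCRF rule, both channels feed the same two categories. Only the sentence in 8.3.1 points the other way.

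**What to change.** 1. In SAP 6.1, replace or supplement the withdrawal item with *Adverse events (serious and nonserious) leading to study drug discontinuation*, by system organ class, preferred term and treatment group, split by seriousness. Add a matching by-patient listing.
2. Define treatment-emergent for all collected AEs, and align SAP 4.2.1 with protocol 9.2.
3. Reconcile the wider sentence in protocol 8.3.1 with footnotes k and l and with Appendix 2. Then retitle or footnote the overview and all-AE tables as serious AEs plus nonserious AEs leading to discontinuation. List any other questionnaire-reported AEs separately and do not discard them. A footnote saying that other AEs were not collected should wait for this step, because it would be false on the wider reading.
4. State how missing causality will be shown in the relatedness table for nonserious events reported by questionnaire.

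The cost is SAP wording, one clarification of the protocol text, and programming of one table and one listing before database lock. Both event categories are already recorded, so no new data collection or design change is needed.

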6.2. Laboratory Data

Laboratory values from non-protocol specified laboratory assessments performed at a local laboratory will be listed in a by-patient listing.

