1.3. Schedule of Activities

NOTE: During the discontinuation phase of the study, questionnaires will be collected until early termination/end of study to collect safety information. Other assessments may be performed at the discretion of the Investigator.

Assessment/Procedure	Responsible Party	Screening ^a (28 days before Day 1)	Day 1	Study Treatment Period ^b (Months)					Early Termination/ End of Study ^c
				3	6	9	12	Every 3 Months	
Informed consent	Investigator	X							
Inclusion and exclusion criteria	Investigator	X							
Demographics	Investigator	X							
Physical examination ^d	Investigator	X							
Vital signs ^e	Investigator	X							
Weight and height ^f	Investigator	X							
12-lead ECG	Recruiting physician (if not done within 6 months prior to screening, see Section 8.2.1.3)	X							
Medical history (including detailed prostate cancer history, current prostate cancer disease status and treatment at study entry)	Patient-reported (Baseline questionnaire)	X							
	Recruiting physician								
Family history of cardiovascular disease	Patient-reported (Baseline questionnaire)	X							

Protocol Amendment 2

Assessment/Procedure	Responsible Party	Screening ^a (28 days before Day 1)	Day 1	Study Treatment Period ^b (Months)					Early Termination/ End of Study ^c
				3	6	9	12	Every 3 Months	
Testosterone	Investigator (if not done within 6 months prior to screening, see Section 8.2.1.4)	X							
	Investigator			6 weeks after start of study treatment, every 6 months thereafter, and at time of PSA rise (Section 8.2.1.4).					
Serum PSA	Investigator (if not done within 6 months prior to screening, see Section 8.2.1.4)	X							
Baseline questionnaire	Patient-reported	X							
PROMIS Short Form V2.0 – Cognitive Function 8a ^g	Patient-reported	X		Every 12 months on study.					
Randomization	Investigator		X						
Study intervention administration: leuprolide acetate or relugolix ^h	Investigator		X ⁱ	Administered as per label.					
Standard of care visit ^j	Investigator			X	X	X	X	X	X ^c
Follow-up questionnaires ^k	Patient-reported			X	X	X	X	X	X
Early discontinuation / End of study questionnaire	Patient-reported								X

Protocol Amendment 2

Assessment/Procedure	Responsible Party	Screening ^a (28 days before Day 1)	Day 1	Study Treatment Period ^b (Months)					Early Termination/ End of Study ^c
				3	6	9	12	Every 3 Months	
Selective safety data ^l	Patient-reported (Follow-up questionnaire)	X		X	X	X	X	X	X
	Investigator		X (see Section 8.3)						

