8.2. Safety Assessments

Study assessments of safety include serious adverse events, nonserious adverse events leading to discontinuation of relugolix or leuprolide acetate (Section 8.3), and clinical laboratory tests as obtained per standard of care (Section 8.2.1.4). Planned time points for all safety assessments are provided in the SoA (Section 1.3).

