8.2.1.4. Clinical Safety Laboratory Assessments

If a patient has not had a testosterone level assessed six months prior to screening, then a testosterone level must be obtained from a local laboratory and submitted with the ERF. Testosterone levels also should be obtained and submitted 6 weeks after the first dose of either relugolix or leuprolide acetate and then every 6 months that the patient remains in the trial. Testosterone levels also should be obtained and submitted when a patient has a rising prostate-specific antigen (per the investigator's judgement). Testosterone levels are being checked to make sure that the patient is in the castrate range. A testosterone concentration above the castrate level (≥ 50 ng/dL) requires evaluation. Specifically, the investigator should first determine whether the patient is compliant with their medication; if compliant, additional evaluation should include repeat measurement of serum testosterone. Given the potential for variability with immunoassays, consider evaluation of testosterone using a liquid chromatography tandem mass spectrometry (LC-MS/MS) assay. If upon repeat testing the patient has persistently elevated testosterone above the castrate threshold, a discussion with the medical monitor should occur.

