6. SAFETY ANALYSES

Safety analyses will be performed on the safety population including summary of adverse event, serious adverse events, laboratory data, and vital signs.

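### SAP 6 promises a laboratory summary, but SAP 6.2 specifies no output that covers the testosterone tests the protocol schedules in both arms

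*SAP*

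**What the plan says.** **Protocol.** Section 8.2.1.4, which is headed as safety laboratory assessments, asks for testosterone in both arms: "Testosterone levels also should be obtained and submitted 6 weeks after the first dose of either relugolix or leuprolide acetate". It then asks for a value every six months and whenever PSA rises. The Schedule of Activities carries the same time points. At screening, if there is no result from the previous six months, "then a testosterone level must be obtained from a local laboratory and submitted with the ERF". The section also sets an action threshold: "A testosterone concentration above the castrate level (≥ 50 ng/dL) requires evaluation". Protocol 8.2 counts laboratory tests among the safety assessments and cross-refers to 8.2.1.4 for them. Protocol 9.2 states: "Safety population will be used to analyze other safety data including treatment-emergent adverse events and clinical laboratory tests as obtained per standard of care".

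**SAP.** Section 4.2.1 repeats that laboratory tests will be analysed in the safety population. Section 6 describes the safety analyses as "including summary of adverse event, serious adverse events, laboratory data, and vital signs". Section 6.2 is the only place where a laboratory output is specified: "Laboratory values from non-protocol specified laboratory assessments performed at a local laboratory will be listed in a by-patient listing".

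**Discontinuation phase.** The Schedule of Activities and protocol 8.2.1 make assessments other than questionnaires discretionary in this phase. That includes testosterone.

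**The concern.** The qualifier *non-protocol specified* in SAP 6.2 restricts the listing to tests that the protocol did not ask for. Testosterone is the only laboratory test with scheduled post-baseline time points; PSA is marked at screening only. The one specified laboratory output therefore excludes the one test to which the protocol's laboratory commitment points.

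The remaining objective is to describe safety. The protocol says that testosterone is checked to confirm castration, and that a value at or above the threshold leads first to a check of whether the patient is taking the medication. One arm takes an oral drug mailed to the home; the other receives depot injections whose dates the investigator records. A report that cannot say how many patients in each arm were at or above 50 ng/dL at each time point omits information the protocol asked sites to submit. Two programmers working from the same SAP could also deliver different outputs.

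**Working it through.** The plan gives no figure to reproduce. The check is a comparison of sections, with a small count for scale.

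**Step 1. Is testosterone protocol-specified?** Yes. Protocol 8.2.1.4 and the Schedule of Activities give time points, a threshold and a request to submit the result.

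**Step 2. Does the local-laboratory condition in SAP 6.2 exclude it?** No. The protocol names a local laboratory for the screening sample and no central laboratory. Only the *non-protocol specified* qualifier excludes it.

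**Step 3. Does another section supply the output?** SAP 6 and 4.2.1 state an intention without specifying an output. SAP 4.1 gives general rules for summarising variables by visit where appropriate, but names no laboratory test. Protocol 9.3 has other baseline data listed, which could catch the screening value but nothing later. Testosterone is not mentioned in the SAP text available; the front matter and the schema figure could not be seen.

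**Step 4. Which values are covered?**

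| Testosterone value | Status in protocol | SAP 6.2 read literally | SAP 6.2 if discretionary tests count as non-protocol specified |
|---|---|---|---|
| Screening | Specified | Not covered (protocol 9.3 may list it) | Same |
| Week 6 and six-monthly, before the discontinuation phase | Specified | Not covered | Not covered |
| At PSA rise, before the discontinuation phase | Specified | Not covered | Not covered |
| Any, during the discontinuation phase | Scheduled but discretionary | Not covered, or unclear | Listed, not summarised |

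**Step 5. Scheduled on-treatment values per patient in 12 months.** Six weeks is 42 days, and 42 / 30.4 = 1.4 months.
- Six-month interval counted from week 6: months 1.4 and 1.4 + 6 = 7.4. The next is 13.4, so there are 2 values by month 12.
- Six-month interval counted from Day 1: months 1.4, 6 and 12, so 3 values.

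Samples at PSA rise are additional. Read literally, SAP 6.2 outputs none of these.

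**Step 6. When did testosterone become discretionary?** The relaxation belongs to the discontinuation phase created by Amendment 2, which SAP 1 dates 29 Feb 2024. Protocol 5.1 makes entry conditional on re-consent, and Appendix 1 requires ethics approval before an amendment is implemented. The date 04 Dec 2023 is when sites were told to stop enrolment. From 04 Dec 2023 to 29 Feb 2024 is 27 + 31 + 29 = 87 days. A cut-off at the earlier date would therefore label at least 87 days of scheduled samples as optional.

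**The case against.** The best counter-argument is that the SAP implements Amendment 2, under which these tests are no longer required, and that protocol 8.2 and 9.2 describe laboratory tests as obtained per standard of care. On that view, testosterone has become a non-protocol test at a local laboratory and 6.2 does list it. This stands for discretionary values in the discontinuation phase at most. The safety population is everyone randomised and treated, so it includes values submitted on schedule earlier, and the current protocol still carries the schedule. If the sponsor intends the wider reading, 6.2 has to say so.

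A second argument is that the word summary in SAP 6 is loose: the same sentence promises a summary of vital signs, and SAP 6.3 provides only a listing. This has some force. It weakens the case that a table was firmly promised, but it does not supply even a listing for scheduled testosterone.

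A third is that the study is terminated, with no formal primary or secondary analysis. SAP 3 nevertheless retains safety analyses, and the change proposed is descriptive. The argument does count against making confidence intervals mandatory.

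Three stronger readings are tempting, and the documents support none of them:
- *The data are lost or unused.* An output that is not specified is not lost data. The protocol has the investigator act on high values and, if they persist, discuss them with the medical monitor, whatever the SAP tabulates.
- *Loss of castration is the main treatment-failure safety signal.* The risk table in protocol 2.3.1 does not list it, protocol 8.1 and 8.6 rule out efficacy and pharmacodynamic assessments, and SAP Table 1 characterises the endpoint by adverse events.
- *Testosterone is the only objective adherence check.* Pill counts (protocol 6.2) and injection dates (protocol 6.4) are also collected. SAP 5 specifies no output for those either.

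**Conclusion.** The concern holds as an internal contradiction with a practical consequence. SAP 6 promises a laboratory summary, while the only specified laboratory output is a listing whose wording excludes the protocol's scheduled test. It should not be read as a decision by the sponsor to suppress testosterone results.

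The size is 2 scheduled on-treatment values per patient in the first 12 months (3 on the Day 1 reading), plus samples at PSA rise, with no specified output. The documents state neither achieved enrolment nor the proportion tested, so the precision of any resulting percentage cannot be judged.

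The conclusion assumes that *non-protocol specified* has its ordinary meaning, that no separate document such as table shells fills the gap, and that sites submitted on-schedule values before patients entered the discontinuation phase. It is worth correcting before database lock, but it affects the completeness of a descriptive safety report, not any formal inference.

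**What to change.** Amend SAP 6.2 as follows:

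- **Listing.** List all testosterone values by patient, with arm, date, time point and a flag for scheduled, unscheduled or PSA-rise samples. Keep the existing listing of other local tests.
- **Summary.** Describe testosterone by arm at baseline, week 6 and each six-month time point, showing the number tested and n (%) at or above the protocol's own 50 ng/dL threshold, with the number tested as denominator. Confidence intervals are optional.
- **Selection.** Keep unscheduled and PSA-rise samples out of the by-time-point percentages, because they are taken for cause.
- **Timing.** Define the windows from first dose, as the protocol does for week 6; SAP 4.3.2 counts study days from randomisation. State whether the six-month interval runs from week 6 or from Day 1.
- **Discretionary period.** State that testosterone became discretionary for each patient on entry to the discontinuation phase under Amendment 2, after re-consent, and not from 04 Dec 2023. Warn that later values may be sparse and selective.

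As a minimum, if the sponsor does not want a table, list testosterone explicitly, remove laboratory data from the summaries promised in SAP 6 and give the reason.

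The cost is one table and one listing on data the protocol already asks sites to submit. The downside is incomplete later values: showing the number tested makes the gap visible but does not remove the selection. No clinical rule changes.
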